8.6.4. Safety

8.6.4.1. Analysis Population

Statistical analyses will be based on all patients who enroll in the study (defined as having an available date of informed consent) and receive at least one within-study dose of Plegridy. Safety analyses will be conducted separately between Plegridy-naïve patients and those who had exposure to Plegridy prior to study enrollment. The definitions will be further described in the SAP.

8.6.4.2. Methods of Analysis

The incidence and incidence rate of all reported SAEs and AEs will be summarized by Medical Dictionary for Regulatory Activities (MedDRA) system organ class and preferred term. Incidence is defined as the proportion of patients with a given event out of the number of patients in the analysis population. Incidence rate is defined as the number of patients with a given event adjusted for the duration of follow-up for the particular event (e.g., incidence rate per 100,000 per years). Ninety-five percent CIs for incidence and incidence-rate point estimates will be calculated using the binomial distribution and the Poisson distribution, respectively.

Incidence of SAEs and AEs will be stratified by event severity and by relationship to treatment with Plegridy. AEs leading to discontinuation of Plegridy will be summarized separately. Analyses of SAEs and AEs may also be described by characteristics of the sites, Prescribing Physicians, and/or patient subgroups defined by appropriate demographic and/or baseline prognostic factors, and/or concomitant medication exposure (e.g., concomitant MS therapies). Analyses may also be stratified by duration of Plegridy treatment or study duration. Specific subgroup analyses will be described in the SAP.

8.6.5. Effectiveness

8.6.5.1. Analysis Population

The population for analysis includes all enrolled patients with informed consent who meet the eligibility criteria and receive at least one within-study dose of Plegridy.

CONFIDENTIAL

The information contained herein may not be used, disclosed, or published without the written consent of Biogen MA Inc.

8.6.5.2. General Methods of Analysis

All computations and generation of tables, listings, and data for figures will be performed using SAS[®] version 9.3 or higher (SAS Institute; Cary, NC).

The SAP will be fully described in a written and approved document. In general, descriptive analyses will be performed to gain a better understanding of the qualitative and quantitative nature of the data collected and the characteristics of the sample studied. Categorical variables will be summarized as number and proportion of the total study population and by subgroups where appropriate. Continuous variables will be reported as mean (and SD) or median and range, where appropriate. Additional exploratory analyses may be performed and will be outlined in the SAP prior to analysis.

Full details on handling of all missing data, which are common in observational studies, will be described separately in the SAP. In general, missing data will not be imputed and the data will be analyzed as they are recorded in the eCRFs. However, if more than 10% of data is missing for one or more key variables, the impact of missing data on the analysis will be discussed, and the pattern of missing data will be explored.

8.6.5.3. Primary Endpoint Analysis

cNEDA will be assessed by the proportion of patients free from measured clinical disease activity (no relapses and no disability progression) and will be summarized over time (e.g., baseline to year 1, baseline to year 2, etc.) as well as from specific time intervals (e.g., from year 1 to year 2, etc.) along with 95% CIs for the proportion.

Analyses of cNEDA may also be described by characteristics of the sites, Prescribing Physicians and among patient subgroups defined by appropriate demographic and/or baseline disease characteristics and prognostic factors. Specific subgroup analyses will be described in the SAP.

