8.3.6. Effectiveness

The following clinical tests/assessments will be collected to evaluate the effectiveness of Plegridy, if performed under routine clinical practice:

- MS relapse information (e.g., date of onset, date of visit, neurologic examination, duration, new and/or recurrent neurologic symptoms, hospitalization, treatments including steroids), if applicable. For the purposes of this study, relapse is defined as new or recurrent neurologic symptoms not associated with fever, lasting at least 24 hours. New or recurrent neurologic symptoms that evolve gradually over months are to be considered disease progression, not an acute relapse. New or recurrent neurological symptoms that occur fewer than 30 days following the onset of a relapse as defined above are to be considered part of the same relapse.
- EDSS information (including Functional System Scores and Ambulation scores), based on neurological examination, when collected as part of routine clinical practice (i.e. not specifically performed for the study).
- Neurologic assessment, if EDSS is not used in routine clinical practice.
- [REDACTED]
- [REDACTED]
- Details of MS-related hospitalizations (e.g., dates of admission and discharge, reason for admission)
- MRI results (e.g., lesion counts, new lesions/ no new lesions), if available
- Ambulation status during follow-up

Refer to Section 16.1 for the timing of assessments.

CONFIDENTIAL

The information contained herein may not be used, disclosed, or published without the written consent of Biogen MA Inc.

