8.6.7. Sample Size Considerations

While no formal statistical hypotheses are being tested in this descriptive observational study, 1100 patients newly or currently prescribed with Plegridy are being targeted for enrollment. All patients will be followed for up to five years, and follow-up is planned regardless of whether patients discontinue treatment with Plegridy. Because this is a long-term observational program, a sample size of 1100 patients was chosen to ensure a reasonable likelihood of observing rare AE events over a 5-year period and to provide informative CIs for SAE incidence and incidence rate point estimates. Based on the withdrawal/discontinuation rates observed in the Plegridy Phase III clinical trial (Study

CONFIDENTIAL

The information contained herein may not be used, disclosed, or published without the written consent of Biogen MA Inc.

105MS301, 1-year) and prior Biogen observational studies, it is expected that approximately 3520–3960 person-years of follow-up will accrue.

With a sample size of 1100 patients, the probability of observing an event with an incidence rate of 0.10% (1/1000 persons) will be approximately 67%; the probability of observing an event with an incidence rate of 0.09% (90/100,000 persons, or 1/1111 persons) will be approximately 63%; the probability of observing an event with an incidence rate of 0.08% (80/100,000 persons, or 1/1250 persons) will be approximately 59%; and the probability of observing an event with an incidence rate of 0.054% (54/100,000 persons, or 1/1851 persons) will be approximately 48%.

For the co-primary endpoint of cNEDA, assuming a dropout rate up to 20%, a sample size of 1100 patients, and an expected 68.4% of patients free from clinical disease activity at the end of one year (Study 105MS301, 1-year), a two-sided 95% CI for the observed proportion of patients free from measured clinical disease activity at the end of one year using large sample normal approximation will extend 0.027 to 0.031 from the observed proportion for an expected proportion of 0.684.

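### The co-primary cNEDA is a crude proportion that takes no account of unequal follow-up, and the protocol's denominator for it is inconsistent

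*Protocol*

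**What the plan says.** Section 8.6.5.3 of the protocol: "cNEDA will be assessed by the proportion of patients free from measured clinical disease activity (no relapses and no disability progression". The proportion is given from baseline to Year 1, Year 2 and so on, and for single-year intervals, with 95% CIs. No method for incomplete follow-up is named.

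The surrounding rules are these:

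- **Population (8.6.5.1):** all eligible, consented patients with one dose during the study. Neither a minimum follow-up nor an EDSS is required.
- **Denominator and missing data (8.6.5.2):** categorical variables are expressed relative to the total study population. "In general, missing data will not be imputed and the data will be analyzed as they are recorded in the eCRFs". Details are left to the SAP. If more than 10% of a key variable is missing, the impact is to be discussed and the pattern explored.
- **Withdrawal (8.2.4.11; Table 4, footnote 3):** nothing further is collected after a patient leaves the study.
- **EDSS (8.3.6):** the protocol collects "EDSS information (including Functional System Scores and Ambulation scores), based on neurological examination, when collected as part of routine clinical practice"; other sites record a neurologic assessment. Section 8.6.5.4 defines progression by EDSS change only, and Section 16.1 mandates no examination.
- **Follow-up and precision (8.6.7):** "approximately 3520–3960 person-years of follow-up will accrue". The cNEDA precision is worked out for one year only, with 1100 enrolled and at most 20% lost; the interval "will extend 0.027 to 0.031 from the observed proportion for an expected proportion of 0.684".
- **Sustained progression (8.6.5.4):** time to this endpoint is analysed by Kaplan-Meier.

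**The concern.** The co-primary objective in Section 7.2 is long-term effectiveness, so the later cumulative figures matter most. A simple proportion from baseline to Year 5 is well defined only if everyone is followed for five years or the plan says how those who are not enter the numerator and denominator. The protocol's own person-years rule out complete follow-up, and its two indications of the denominator disagree. The reported Year-5 value could then depend more on the handling of dropouts than on disease activity. The composite would also be handled less well than its own progression component, for which the protocol already uses a method that allows for censoring.

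The EDSS question is separate. A patient with no EDSS cannot meet the only definition of progression, yet belongs to the analysis population. If such patients are classed as free whenever they are relapse-free, the error can only be upward.

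**Working it through.** **1. The plan's own figure.** Inputs from Section 8.6.7: p = 0.684, N = 1100, dropout up to 20%, two-sided 95%. Half-width = 1.96 × √(p(1 − p)/n).

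- n = 1100: 1.96 × √(0.684 × 0.316/1100) = 0.0275
- n = 1100 × 0.8 = 880: 1.96 × √(0.684 × 0.316/880) = 0.0307

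The stated 0.027 to 0.031 reproduces. The upper value is obtained only by taking dropouts out of the denominator, which is not the total-population denominator of Section 8.6.5.2.

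**2. Implied retention.** Mean follow-up is 3520/1100 = 3.2 to 3960/1100 = 3.6 years. With a constant dropout hazard h (assumption), (1 − e^(−5h))/h equals the mean follow-up.

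- 3.2 years: h = 0.194 per year; retained at Year 5 e^(−5h) = 0.379
- 3.6 years: h = 0.139 per year; retained at Year 5 = 0.498

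Annual loss is 17.6% and 13.0%, which fits the 20% in Section 8.6.7 as a one-year ceiling. If 20% were the five-year total, about 4930 person-years would accrue, which contradicts the stated range.

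**3. Effect of the denominator.** Activity hazard λ = −ln(0.684) = 0.380 per year, held constant for five years and independent of dropout (assumptions). Write E(t) = λ/(λ + h) × (1 − e^(−(λ+h)t)) for the share with a recorded event by t, and F(t) = e^(−(λ+h)t) for the share event-free and still followed.

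- True value: e^(−λt)
- All treated, dropouts counted as free: 1 − E(t)
- Recorded events plus event-free completers: F(t)/(F(t) + E(t))
- Completers only: F(t)/e^(−ht) = e^(−λt)

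For example, at Year 5 with h = 0.194: E = 0.662 × (1 − 0.057) = 0.624, so all treated gives 0.376, and events plus completers gives 0.057/(0.057 + 0.624) = 0.083.

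| Year | True | All treated | Events + completers | Completers only |
|---|---|---|---|---|
| 1 | 0.684 | 0.704–0.711 | 0.661–0.668 | 0.684 |
| 2 | 0.468 | 0.527–0.548 | 0.413–0.428 | 0.468 |
| 3 | 0.320 | 0.423–0.457 | 0.248–0.267 | 0.320 |
| 5 | 0.150 | 0.323–0.376 | 0.083–0.099 | 0.150 |

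At Year 1 the error is +2.0 to +2.7 points or −1.6 to −2.3 points, against a half-width of about 3 points. At Year 5 it is +17 to +23 points or −5 to −7 points.

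**4. Sensitivity.**

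- Slower course, assumed true Year-5 value 0.30: all treated 0.46–0.51, events plus completers 0.19–0.22. With 0.40: 0.55–0.59 and 0.27–0.31.
- Completers only, with the dropout hazard 1.5–2 times higher after activity: 0.18–0.24 at Year 5 instead of 0.150.

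**5. Missing EDSS.** Let m be the share without EDSS and s the share of the activity hazard due to progression alone. The documents give neither. If these patients are counted as free when relapse-free, the proportion becomes (1 − m)e^(−λt) + m e^(−λ(1−s)t). For m = 10–50% and s = 10–30% (both assumed), the excess is 0.3–4.1 points at Year 1 and 0.3–5.7 points at Year 5.

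**The case against.** The strongest reply is that Section 8.6.5.2 leaves missing-data handling to the SAP, which is not among the documents here. The SAP could define evaluable patients or add a censoring rule, and the protocol does not forbid either. This limits what can be said about the final analysis. It does not remove the point: the protocol itself names the estimator, the population and a default of no imputation, and its two denominators disagree. The 10% clause prompts discussion and changes no estimate.

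A reader might infer that dropouts will be counted as free, so that Year-5 cNEDA is bound to be inflated to 32–38%. The documents do not support that. The total-population wording is generic, counting an unobserved patient as free sits badly with no imputation, and the one calculation specific to cNEDA removes dropouts. Completers only would be unbiased if dropout is independent of activity.

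A reader might likewise infer that patients without EDSS are counted as free when relapse-free. No sentence says so; the composite could equally be treated as missing for them.

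It also stands that the 15% extrapolates a one-year figure, that the single-year intervals limit accumulated attrition, and that the study is descriptive with no formal hypothesis tests.

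**Conclusion.** The concern holds in a conditional form. The protocol sets a long-term co-primary endpoint as a crude proportion that does not allow for unequal follow-up, although its own person-years imply that half or more of the patients are no longer followed at Year 5. Direction and size of the error depend on a denominator that it leaves inconsistent. Against a true 15%, the readings run from 8–10% through about 15% to 32–38%. At Year 1 the error is about 2 points either way. These figures rest on constant hazards, dropout independent of activity, and extrapolation from 68.4%; with a slower disease course the gap between readings remains wide. The EDSS bias is upward if patients without EDSS are counted as free, but the documents do not allow its size to be fixed.

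**What to change.** Make the primary cNEDA estimate the Kaplan-Meier probability of remaining free of first relapse or EDSS progression at each year, with a 95% CI.

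- **Population:** treated patients with a baseline EDSS, accepting the latest pre-enrollment EDSS already collected under Section 8.3.2. Do not require a later EDSS: that conditions on future follow-up and would drop patients who relapse and leave.
- **Events:** count every recorded relapse or progression, including relapses after the last EDSS.
- **Censoring:** censor event-free patients at the last EDSS assessment or end of follow-up. State which applies and run the other as a check, because the first can pull the estimate down when later relapses still count and the second can miss unassessed progression.
- **Yearly intervals:** use patients event-free and under follow-up at the start of the interval.
- **Supportive analyses:** relapse-free Kaplan-Meier estimates in all treated patients, including those without EDSS; the crude proportion with its denominator stated; and a sensitivity analysis for informative dropout, since Kaplan-Meier also assumes that censoring is unrelated to activity.

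Sections 8.6.5.2 and 8.6.7 should then give the same denominator. The change is one of protocol and SAP wording and needs no new data. Its cost is a smaller denominator and wider CIs.

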8.6.5.4. Secondary Endpoints Analysis

Plegridy prescription and utilization

Duration of Plegridy use and prescribed dosing frequency will be summarized both descriptively and categorically, as appropriate. Primary reasons for discontinuation of Plegridy will be tabulated. Plegridy use will also be described by concomitant medications.

Clinical disease activity (relapse activity and disability progression)

Relapse activity will be assessed by evaluating by relapse-related endpoints. These analyses will include the following parameters:

- ARR: defined as the total number of relapses divided by the number of patient-years on study divided by 12 months.
- Time to first relapse: defined as time (in days) between the date of initiating Plegridy to date of onset of first relapse following Plegridy initiation. Please refer to Section 8.3.6 for the definition of relapse.

CONFIDENTIAL

The information contained herein may not be used, disclosed, or published without the written consent of Biogen MA Inc.

- Proportion of patients with relapse: The proportion of patients with relapse will be described by counts and percent.
- Distribution of the number of relapses: The distribution of the number of relapses will be summarized using mean (SD) and median (minimum and maximum).

Disability progression will be assessed by evaluating disability progression-related endpoints. These analyses will include the following parameters:

- Proportion of patients with sustained progression for at least six months. For the purposes of this study, progression is defined as at least a 1.0 point increase from baseline in EDSS ≥ 1.0 or at least a 1.5 point increase from a baseline EDSS = 0.
- Time to sustained progression for at least six months.

ARR will be analyzed using a negative binomial model, adjusted for appropriate prognostic factors. If the data are under-dispersed or if the negative binomial regression model does not converge, a Poisson regression model with the same covariates will be used instead. Time to sustained progression will be analyzed using Kaplan-Meier estimates.

In addition, Poisson regression model and Cox proportional hazard model might be applied to assess the association between certain demographic variables, baseline disease characteristics, or medical history variables of interest and ARR/time to sustained disability progression, respectively.

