8. RESEARCH METHODS

8.1. Study Design

POP is a prospective, global, observational study designed to provide long-term effectiveness and safety data in patients with RMS who have been prescribed Plegridy in routine clinical practice.

Plegridy will not be supplied for this study. The study will collect data in an observational manner from patients who are prescribed Plegridy by physicians, according to the approved label in the respective country.

Based on Version 3.0 of this protocol, dated 02 February 2016, enrollment was to be continued until July 2017, when approximately 1600 patients with RMS who are newly or currently prescribed treatment with Plegridy were planned to be enrolled.

Approximately 160 sites in multiple regions, including the US, the EU, Australia, and sites participating in Study 105MS302 or 105MS303 in other countries, were to participate. Enrollment was to be competitive to provide for the highest likelihood of enrolling the targeted number of patients in a 33-month period. In January 2017, following a decision by Biogen to limit enrollment to approximately 1100 patients, a Protocol Clarification Letter was sent to all study sites providing official notification that enrollment into the study should be stopped. Enrollment was ended in January 2017 after a 27-month period.

Patients are to be followed (regardless of discontinuation of Plegridy) for a maximum of 60 months or until death, withdrawal from study, or loss of follow-up, whichever occurs first. Data are to be collected at baseline and every three months during the first year of follow-up, then every six months in Year 2 through Year 5.

[figure not shown]
The POP is a prospective observational study designed with the potential to combine with other similar longitudinal studies of MS. While no such cross-study analysis has been undertaken to date, the POP will provide an additional complementary and supplementary data-set to bolster future studies of MS and its treatment options.

[Figure 1](#) below presents a schematic of the prospective observational study of patients with RMS prescribed Plegridy.

CONFIDENTIAL

The information contained herein may not be used, disclosed, or published without the written consent of Biogen MA Inc.

Figure 1: Study Design

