8.1.2. Secondary Endpoints

Secondary endpoints will address non-serious AEs of special interest and other clinical effectiveness and non-safety related objectives as follows:

- Plegridy prescription and utilization patterns will be evaluated by assessment of prescribed dosing frequency, duration of Plegridy use, and primary reason for discontinuation of Plegridy (see Section 8.3.3 “MS Treatments and Concomitant Medications”).
- Effectiveness of Plegridy on specific MS clinical disease activity will be evaluated by assessment of relapse-related endpoints (e.g., ARR, time-to-first relapse, proportion of patients with relapse, and distribution of number of relapses and disability progression-related endpoints based on the EDSS (e.g., proportion of patients with progression and time-to-sustained progression for at least six months).

CONFIDENTIAL

The information contained herein may not be used, disclosed, or published without the written consent of Biogen MA Inc.

- Safety and tolerability of Plegridy will be assessed by the incidence proportion and incidence rates of non-serious AEs, including but not limited to FLS, ISRs, and AEs (including laboratory abnormalities) leading to treatment discontinuation.
- The impact of the severity of FLS on the ability to successfully manage symptoms via prophylaxis will be evaluated using the patient-reported FLS-VAS.
- Changes in FLS assessment and FLS-VAS over time.
- Changes in HRQoL measures will be evaluated over time using the EQ-5D-3L.
- Healthcare resource consumption will be evaluated by assessment of endpoints such as MS-related and non-MS-related physician visits, specialists' visits, use of physiotherapy, hospitalizations and lengths of stay, and emergency room (ER)/department visits.
- Patient-reported treatment adherence to Plegridy will be assessed using the Treatment Adherence Questionnaire for all patients.

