8.2. Setting

8.2.1. Inclusion Criteria

To be eligible to participate in this study, patients must meet the following eligibility criteria at the time of enrollment:

1. Patient and or legal representative is willing and able to understand the purpose and risks of the study and provide signed and dated informed consent and authorization to use protected health information (PHI) in accordance with national and local patient privacy regulations.
2. Patient with MS who is newly, or is currently, prescribed Plegridy according to local label including patients who participated in Study 105MS302 or Study 105MS303.
3. Patient age 18 years or older.
4. Patient willing and able to complete PROs with minimal assistance.

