8.6.3. Demography and Baseline Disease Characteristics

Demographic and baseline disease characteristics will be summarized overall. The demographic profile (age, sex, and race [where legally allowed]), relevant medical history, MS disease history, MS treatment prior to start of Plegridy, and concomitant medications and therapies used will be listed and summarized using appropriate descriptive statistics for categorical and continuous variables. Categorical variables will be summarized using frequencies and percentages. Continuous variables will be summarized using mean, SD, median, and maximum and minimum values. Two-sided

CONFIDENTIAL

The information contained herein may not be used, disclosed, or published without the written consent of Biogen MA Inc.

95% CIs will be used. In general, categorical data will be summarized using frequency and percentage, and continuous variables will be summarized using descriptive statistics (number, mean, SD, median, minimum, and maximum). For continuous variables, if the data are approximately normally distributed, then a 95% CI for the mean change will be calculated. If the data are not normally distributed, then the interquartile range will be presented with the median. All analyses will be conducted using a two-sided test and a significance level of 0.05. Due to the inherent differences in Plegridy-naïve patients and those who had exposure to Plegridy prior to study enrollment, analyses will be conducted separately for these two groups. The definition of Plegridy-naïve will be described in the SAP.

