Longitudinal evaluation of continuously measured secondary endpoints (e.g., EQ-5D-3L and FLS) may be performed using a linear regression model to evaluate the long term experience (e.g. change over time) of patients regarding these measures while on Plegridy. Categorical outcomes on healthcare resource consumption, treatment adherence, [REDACTED] and Plegridy prescription and utilization patterns will be summarized using frequencies and percentages. If necessary, a 95% CI based on binomial distribution might be provided for some of the categorical variables like patient adherence.

FLS-VAS includes the patients' ratings of effectiveness and satisfaction of controlling FLS with prophylactic regimens. The ratings will be summarized by mean (SD) and median (maximum and minimum). Changes of FLS-VAS ratings over time will also be summarized by mean (SD) and median (maximum and minimum). The changes of FLS-VAS ratings over time will be tested using a Wilcoxon rank-sum test. Longitudinal evaluation of FLS-VAS ratings using a linear regression model may be performed to evaluate patients' long-term experience (e.g., change over time) with the effectiveness and satisfaction of prophylactic regimens to control FLS while receiving Plegridy.

[REDACTED]

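### Duration of Plegridy use is right-censored, but the protocol plans only plain descriptive and categorical summaries; read as time to stopping, these are too short in naive patients and biased in an unpredictable direction in experienced patients

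*Protocol*

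**What the plan says.** Section 8.1.2 makes utilization a secondary endpoint with three parts: "prescribed dosing frequency, duration of Plegridy use, and primary reason for discontinuation of Plegridy". For the analysis, Section 8.6.5.4 states: "Duration of Plegridy use and prescribed dosing frequency will be summarized both descriptively and categorically, as appropriate". Later in that section: "Plegridy prescription and utilization patterns will be summarized using frequencies and percentages". The general rule in Section 8.6.5.2 is: "Continuous variables will be reported as mean (and SD) or median and range, where appropriate". A time-to-event method is assigned elsewhere in Section 8.6.5.4, but to another endpoint: "Time to sustained progression will be analyzed using Kaplan-Meier estimates".

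On observation time, Section 8.1 says: "Patients are to be followed (regardless of discontinuation of Plegridy) for a maximum of 60 months". It ends earlier at death, withdrawal or loss. Section 8.2.1 admits both new and existing users: "Patient with MS who is newly, or is currently, prescribed Plegridy according to local label". Section 8.6.3 has the naive and experienced groups analyzed separately. Section 8.2.4.9 allows patients who stop to restart. The protocol does not say how ongoing use at last contact enters the duration summary, or from which date duration runs in experienced patients.

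**The concern.** Duration of use is complete only for patients seen to stop. For everyone else, the recorded value is the time on drug so far. A mean, SD, median or range treats that value as final. Categories have the same fault: a patient lost at 18 months while still on drug falls into an under-2-years class although the true duration is unknown.

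The endpoint stands beside the reason for discontinuation, and Section 6.3 motivates the study partly by factors that lead to discontinuation. A reader will therefore tend to take duration of use as time to stopping. Read that way, the figure depends on how long patients happened to be followed. Section 8.6.6 plans annual interim analyses with results sent to congresses, so the plain figure would tend to rise from one report to the next even if stopping behavior never changed.

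Experienced patients raise a second problem. Those who had already stopped are largely unable to enter, so short durations are under-represented. Analyzing this group separately avoids mixing it with naive patients but does not correct the selection within it.

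**Working it through.** The protocol states no figure for duration of use, so there is none to reproduce. The nearest is the expected follow-up in Section 8.6.7.

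**Step 1: dropout implied by the plan.** 3520/1100 = 3.2 and 3960/1100 = 3.6 years mean follow-up. With a constant dropout hazard L and a 5-year cap, mean follow-up is (1 − e^(−5L))/L. Setting this to 3.2 and 3.6 gives L = 0.194 and 0.139 per year (38% and 50% retained at 5 years).

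**Step 2: naive patients, closed form.** Assume exponential stopping with hazard h. Observed duration is the earliest of stopping, dropout and 5 years. Its median is ln 2/(h + L) when that is below 5. For a true median of 3 years, h = ln 2/3 = 0.231:

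- L = 0.139: 0.693/0.370 = 1.87 years.
- L = 0.194: 0.693/0.425 = 1.63 years.

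The share still on drug when last seen is 1 − [h/(h + L)] × [1 − e^(−5(h + L))], which gives 47% and 52%.

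**Step 3: naive patients over a range of assumed stopping rates.** Simulation of 400,000 patients per scenario; ranges cover the two dropout hazards. Medians in years.

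| Stopping hazard per year | True median | Plain median | Kaplan-Meier median | Still on drug when last seen |
|---|---|---|---|---|
| 0.05 | 13.86 | 2.84–3.65 | not reached | 84–86% |
| 0.10 | 6.93 | 2.36–2.91 | not reached | 71–74% |
| 0.20 | 3.47 | 1.76–2.05 | 3.46–3.47 | 52–56% |
| 0.30 | 2.31 | 1.40–1.57 | 2.31 | 39–44% |
| 0.50 | 1.39 | 0.99–1.08 | 1.38 | 25–30% |

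The plain median is too short in every row. Kaplan-Meier recovers the true median wherever it lies within 5 years.

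**Step 4: experienced patients, plain median counted from first dose.** Entry is assumed uniform over 0 to 0.5, 0 to 2 or 0 to 4 years after first dose, among those still on drug.

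| Stopping hazard per year | True median | Entry within 0.5 y | Entry within 2 y | Entry within 4 y |
|---|---|---|---|---|
| 0.05 | 13.86 | 3.09–3.90 | 3.86–4.67 | 4.93–5.35 |
| 0.10 | 6.93 | 2.61–3.16 | 3.38–3.90 | 4.42–4.93 |
| 0.20 | 3.47 | 2.01–2.30 | 2.77–3.03 | 3.74–4.01 |
| 0.30 | 2.31 | 1.65–1.82 | 2.39–2.54 | 3.24–3.42 |
| 0.50 | 1.39 | 1.24–1.33 | 1.95–2.02 | 2.52–2.61 |

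The figure is short in some cells and long in others. Counted from enrollment instead, it is short in every scenario (for example 1.76 to 2.05 against 3.47 years at hazard 0.20).

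**The case against.** The strongest reply is that the protocol never speaks of persistence. It sets out to describe utilization, and observed exposure is a legitimate descriptive quantity: Section 8.6.4.2 itself allows safety analyses by length of treatment. Read as exposure during observation, a mean or median is not biased. This stands, but only if the result is labelled as observed exposure, and the protocol does not say which quantity it means.

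A second reply is that the qualifier in Section 8.6.5.4 leaves room for a Kaplan-Meier summary, and that details belong in the statistical analysis plan. The wording does not forbid it. Still, the protocol names the type of summary, defines it elsewhere as ordinary statistics or frequencies, and reserves Kaplan-Meier for another endpoint in the same section. That is a choice of method, not silence.

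Third, no formal comparison of duration between naive and experienced patients is planned, and Section 8.2.4.1 already acknowledges that existing users are a selected group. This stands: the point concerns each group's own figure, not a planned contrast.

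A reader might go further and infer that durations in experienced patients must come out too long, perhaps by a factor of two. The documents do not support that. Right-censoring shortens their durations too; only delayed entry lengthens them. The factor of two compares completed durations under a steady state. With a true median of 3 years, mean prior use would be 3/ln 2 = 4.33 years and mean observed further use 2.07 to 2.28 years. The total is 6.40 to 6.61 against 4.33, about 1.5-fold. Even that needs an average of 4.33 years of prior use, which nothing in the protocol supports.

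**Conclusion.** The point holds in a limited form. For naive patients, the planned summary understates time to discontinuation across assumed stopping hazards of 0.05 to 0.50 per year. With a true median of 3 years it gives about 1.6 to 1.9 years. For experienced patients the figure is biased, but its direction depends on the stopping rate, the lag from first dose to enrollment and the time origin, none of which the protocol gives.

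The sizes rest on constant stopping and dropout hazards, on independence between the two, and on dropout inferred from the planned person-years. The direction in naive patients does not depend on the particular rates, because cutting off ongoing use can only shorten it.

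This is a secondary descriptive endpoint. It is worth correcting, but it leaves both primary endpoints and every sample-size and precision figure untouched.

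**What to change.** Keep the present sentence in Section 8.6.5.4 for prescribed dosing frequency and, if wanted, for duration of use labelled as observed exposure. Replacing it outright would drop the dosing-frequency summary. Add text to this effect:

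- Time from first dose to Plegridy discontinuation will be estimated by Kaplan-Meier, separately in naive and experienced patients.
- Naive patients still on Plegridy at last contact are censored there. Experienced patients are timed from first dose, enter the risk set at enrollment (delayed entry), and are censored in the same way.
- The percentage still on Plegridy at years 1 to 5 is reported with 95% CIs. Showing numbers at risk is advisable, since early times in experienced patients and year 5 in naive patients may be thinly covered.
- An analysis rule states how interruptions and restarts are counted, because Section 8.2.4.9 allows restarting.

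No new data are needed. Start and stop dates are collected under Section 8.3.3, and Table 4 (footnote 2) takes data back to first dose for patients with earlier exposure. The cost is one additional secondary analysis. Kaplan-Meier still assumes that leaving the study while on drug is unrelated to imminent stopping, and the report should say so.
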